# 8.2.2 Secondary Objectives

For participants with FOP exposed and unexposed to palovarotene:

- To describe the range of motion (ROM) as assessed by the Cumulative Analogue Joint Involvement Scale (CAJIS) for FOP;
- To describe the use of assistive devices and adaptations for daily living;
- To describe the physical function using age-appropriate forms of the Fibrodysplasia Ossificans Progressiva-Physical Function Questionnaire (FOP-PFQ);
- To describe the parameters of lung function (observed and % predicted forced vital capacity (FVC), observed and % predicted forced expiratory volume in one second (FEV1), absolute and % predicted FEV1/FVC ratio, observed and % predicted diffusion capacity of the lung for carbon monoxide (DLCO)) at Baseline and over time;
- To describe the physical and mental health (participants ≥15 years old) and overall quality of life (QoL) (participants <15 years old) using age-appropriate forms of the Patient-Reported Outcomes Measurement Information System (PROMIS) Global Health Scale;
- To describe the flare-up frequency;
- To describe any movement mobility change by body location and annually;
- To describe the number of locations impacted by movement mobility change per participant annually;
- To describe the movement mobility outcomes (change in extra bone growth and change in movement), causes and associated symptoms if preceded by a flare-up event by body location;
- To describe the frequency, severity, outcome and descriptive details of any fractures (including bone fracture and vertebral fractures).
- To describe the incidence of pregnancy.

For participants with FOP exposed to palovarotene who become pregnant while enrolled in FOPal:

- To describe pregnancy characteristics and outcomes;
- To describe pregnancy-related AEs through the first year postpartum;
- To describe birth and developmental outcomes through the infant(s)' first year of life.

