# 9.1 Registry Study Design

FOPal is an observational, prospective and retrospective registry study designed to collect and assess real-world safety data on paediatric and adult participants with FOP exposed to palovarotene and secondly to describe the effectiveness of palovarotene in exposed participants. Additionally, key safety outcomes (i.e. flare-up episodes, growth and bone fractures) will be descriptively compared in participants with FOP exposed and unexposed to palovarotene enrolled in the FOPal registry.

Exposed and unexposed participants will be recruited in countries/sites willing to participate and where palovarotene is registered/marketed. For exposed participants, the decision to prescribe palovarotene will be made prior to and independently of the decision to enrol the patient in the FOPal registry study.

Participants who started palovarotene treatment before the implementation of the registry study in their country may also be enrolled. All participants who received at least one dose of palovarotene treatment before enrolling in the registry study (i.e. signing the informed consent) will be considered non-naïve. In such context, some data will be collected retrospectively from the first dose of marketed palovarotene intake. A schematic representation of the different data collection scenarios is shown Figure 2.

Figure 2 Schematic representation of the different scenarios applied for prospective and retrospective data collection from participants enrolled in the FOPal registry

The schedule of assessments in Table 2 and Table 3 describes the type of data collected for exposed naïve and non-naïve participants, respectively, from the first dose of marketed palovarotene intake. The schedule of assessments in Table 4 describes the type of data collected for unexposed participants from up to 12 months before the ICF signature. The details are described in the Section 9.2.7.

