**PAGE 41 OF 287** 

 Table 3
 Schedule of Assessments: Exposed Non-naïve Participants

Assessment/Procedure	Retrospective Period (From first marketed palovarotene intake)	Baseline Visit	Follow-Up Visits (as per routine clinical practice[a])/ End of Study Visit
Clinic visit or telephone/video contact visit		X	X
Informed consent [b]		X	
Inclusion/exclusion criteria		X	
Baseline demographics		X	
Physical examination [c,d]	X [p]	X	X
Medical or surgical history	X		
FOP history	X		
Growth status assessment (bone age, knee height and epiphyseal status) [d,e]	X [p]	X	X
Tanner staging	X [p]	X	X
Linear height [f] and weight [d]	X	X	X
Vital signs [d,g]	X [p]	X	X
Pregnancy testing [h]		X	X
Prior /concomitant medications [i]	X	X	X
Concomitant surgery and non-drug therapies	X	X	X
Prior use of palovarotene (investigational product)	X		
Palovarotene dose for chronic and flare-up treatment [j]	X	X	X
Spirometry and DLCO test [d,k]	X [p]	X	X
CAJIS [d]	X [p]	X	X
Movement mobility history (including flare-ups [l])	X		
Movement mobility changes (including flare-ups)		X	X
Spinal health assessment [m]	X [p]		X
Retrospective important medical events related to the disease (including vertebral fractures)	X		
AEs SAEs, Special Situations and AESIs [n]		X	X
Participant Questionnaires:			·
FOP-PFQ assessment [o]		X	X
PROMIS Global Health Scale [o]		X	X
FOP assistive devices assessment [o]		X	X

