**PAGE 42 OF 287** 

AE=Adverse Event; AESI=Adverse Event of Special Interest; CAJIS=Cumulative Analogue Joint Involvement Scale; CT= Computed Tomography; DLCO=Diffusion Capacity of the Lung for Carbon Monoxide; FEV1=Forced Expiratory Volume in one second; FOP=Fibrodysplasia Ossificans Progressiva; FOP-PFQ=FOP-Physical Function Questionnaire; FVC=Forced Vital Capacity; HEENT= head, eyes, ears, nose and throat; PI=Prescribing Information; PROMIS=Patient-Reported Outcomes Measurement Information System; SAE=Serious Adverse Event.

- a Follow-up Visits are recommended every 6 months, or as per local label.
- b If participant <18 years (or the legal age of consent in the jurisdiction in which the study is taking place), assent and parent or legally authorised representative consent will also be required.
- c This includes a general assessment, dermatologic, lymph nodes, HEENT, chest, cardiac, abdomen, limb/extremities, musculoskeletal, neurologic and other.
- d Not expected in the context of a telephone/video visit.
- e Collected for growing children. Assessment as per local label.
- f Linear height within 6 to 12 months prior to first marketed palovarotene intake.
- g Vital signs to be collected are respiratory rate, blood pressure and heart rate.
- h Participants will be assessed for child-bearing status and pregnancy prevention measures. As per local label, pregnancy testing is carried out with a confirmation of absence of pregnancy monthly if the participant receives palovarotene and one month after stopping. These conditions also concern participants who are not currently sexually active unless the prescriber considers that there are compelling reasons to indicate that there is no risk of pregnancy.
- This includes a period of two months prior to the first marketed palovarotene intake.
- j Not applicable for pregnant participants.
- k Spirometry obtains the lung function parameters of observed and % predicted FVC and FEV1 and the absolute and % predicted FEV1/FVC ratio. The DLCO test obtains observed and % predicted DLCO which provides information on the efficiency of gas transfer from alveolar air into the bloodstream.
- 1 This includes number of flare-ups over the past 12 months before the first marketed palovarotene intake.
- m Spinal health assessment to be performed using radiological imaging (e.g. CT, X-ray, scintigraphy, etc).
- n AE, SAE, Special Situation and AESI collection begins once the informed consent has been signed.

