**PAGE 65 OF 287** 

#### Pregnancy

Confirmation of an absence of pregnancy will be included in the participant data listings using the Safety Exposed Population only.

Incidence of all pregnancies will be summarised for those exposed and unexposed to palovarotene in the Safety Exposed Population. For these analyses, the pregnancy will be considered as exposed to palovarotene if it occurs whilst the participant is using the medicinal product or within 2 days after stopping the product (based on the estimated date of conception).

For participants who become pregnant while enrolled in FOPal, whether exposed or not to palovarotene, pregnancy characteristics and outcomes, pregnancy-related AEs through the first year postpartum, and birth and developmental outcomes through the infant(s)' first year of life will be descriptively summarised by palovarotene exposure status (exposed and unexposed).

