### 11.1.3.1 Pregnancy or Breastfeeding

### Pregnancy

Palovarotene is highly teratogenic and must not be used by participants who are or may become pregnant.

In accordance with the label, if pregnancy occurs in a participant exposed to palovarotene, treatment must be stopped immediately, and the participant should be referred to a physician for evaluation and advice. Participants of child-bearing potential must use at least one highly effective method of contraception (e.g. intrauterine device (IUD)) or two effective methods (e.g. combined hormonal contraception in combination with another method of contraception such as a barrier method) during the course of the study.

Pregnancy itself is not regarded as an AE unless there is a suspicion that the product has interfered with a contraceptive method. If pregnancy occurs while enrolled in FOPal, the outcome of the pregnancy will then need to be collected. This applies irrespective of whether the pregnancy is considered to be related to interference with a contraceptive method by the product.

The following maternal, neonatal, and infant outcomes will be assessed:

- Maternal outcomes:
  - Foetal loss: miscarriage, spontaneous abortion, stillbirth, elective or therapeutic abortion, foetal loss type not specified.
- Neonatal outcomes (from birth to one month):
  - Neonatal death with or without congenital abnormalities (major or minor);
  - Live birth with congenital abnormalities (major\* and minor);
  - Live birth without congenital abnormalities;
  - Preterm birth;
  - Small for gestational age.
  - \* Major birth defects are defined as major structural or genetic birth defects as conditions that 1) result from a malformation, deformation, or disruption in one or more parts of the body, a chromosomal abnormality, or a known clinical syndrome; 2) are present at birth; and 3) have a serious, adverse effect on health, development, or functional ability.

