**PAGE 77 OF 287** 

- Infant outcomes (from one month to one year, end of follow-up period):
  - Infant death;
  - Postnatal growth deficiency;
  - Infant developmental delay;
  - Infant hospitalisation due to serious illness.

Details of all pregnancies in participants will be collected from the signing of the ICF and the participant will be followed through the first year postpartum to monitor pregnancy-related AEs, and the birth and developmental outcomes through the infant(s)' first year of life. The following monitoring schedule is recommended for data collection:

- Baseline;
- Mid-pregnancy;
- Estimated Due Date (EDD);
- EDD + 6 months;
- EDD + 12 months.

For live-born infants, data should be assessed at 3 timepoints during the data collection: at EDD; EDD + 6 months; and EDD + 12 months.

Information regarding any pregnancies must be collected on the electronic data collection tool or the "Adverse Event and Other Safety Events Report Form for Company-Sponsored Non-Interventional Studies" (134232-FOR) if the electronic data collection tool is unavailable. Pregnancy information, including birth and developmental status of the infant will also be collected in the Drug Exposure During Pregnancy Form for Company-Sponsored Clinical Studies (458088-FOR) and should be provided for all pregnancies, regardless of the outcome.

Abnormal pregnancy outcomes (such as spontaneous abortion, foetal death, stillbirth, livebirth with congenital abnormalities (major and minor), ectopic pregnancy, termination of pregnancy, preterm birth, small for gestational age or foetal growth restriction, neonatal or infant death, and any other foetal or infant abnormalities that may be medically important) are considered SAEs.

Reports of pregnancy must be reported to Ipsen within 24 hours of the investigator's knowledge.

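### For exposed non-naïve participants, the protocol conflicts on whether pregnancies between first marketed dose and consent are collected, and no section clearly requires their details

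*Protocol*

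**What the plan says.** Section 9.1 lets people enrol after starting treatment and defines the non-naïve group this way: "All participants who received at least one dose of palovarotene treatment before enrolling in the registry study (i.e. signing the informed consent) will be considered" part of it. For this group, "some data will be collected retrospectively from the first dose of marketed palovarotene intake". Section 9.7.1 places them in the Safety Exposed Population as prevalent users.

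On pregnancy, section 11.1.3.1 says "Details of all pregnancies in participants will be collected from the signing of the ICF" and "If pregnancy occurs while enrolled in FOPal, the outcome of the pregnancy will then need to be collected". The outcome objectives in section 8.2.2 have the same scope: "For participants with FOP exposed to palovarotene who become pregnant while enrolled in FOPal". Section 11.1.3.1 also says that pregnancy is not in itself an adverse event unless the product is suspected of interfering with contraception. It nevertheless classes abnormal outcomes, including spontaneous abortion and termination, as serious adverse events.

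Table 3 (non-naïve schedule) has no retrospective mark for pregnancy testing or for adverse events and Special Situations. Its footnote n reads "AE, SAE, Special Situation and AESI collection begins once the informed consent has been signed". The retrospective safety row is labelled "Retrospective important medical events related to the disease (including vertebral fractures"), and section 9.3.2.5 uses the same label.

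Sections 11.2.1 and 11.2.2 are wider. The first collects retrospective adverse events from first marketed dose to consent. The second treats retrospective important medical events as covering serious events, events of special interest, related nonserious events and Special Situations. It has them reported to the sponsor only where no spontaneous report was ever made. Section 11.1.3 makes drug exposure during pregnancy a Special Situation.

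On analysis, section 9.7.3.4 states "Incidence of all pregnancies will be summarised for those exposed and unexposed to palovarotene in the Safety Exposed Population".

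**The concern.** The protocol calls the drug highly teratogenic, and section 7.3.1 records no pregnancies in clinical development. The planned exposed cohort is small (minimum 67), so each exposed pregnancy carries weight.

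For non-naïve participants there is an interval on marketed drug before consent. The registry looks back over that interval for dose, medications, height and flare-ups. Section 9.3.2.7 gives pre-consent fractures an explicit rule and a form of their own, but pregnancy has no matching rule. A site working from Table 3 and section 11.1.3.1 would see no clear duty to record a pregnancy that began and ended in the interval. A site working from section 11.2.2 might record some of them.

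Two things are at stake. Capture could differ between sites and by type of outcome. The incidence of all pregnancies could also be computed over exposed time in which pregnancies were not reliably looked for.

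**Working it through.** The protocol states no figure on this point, so there is none to reproduce. The check is a cross-reading, followed by illustrations on stated assumptions.

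**1. The sections side by side (non-naïve participant, first marketed dose to consent)**

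| Place | Reading for this interval |
|---|---|
| 11.1.3.1, start of pregnancy details | Not collected before consent |
| 11.1.3.1 and 8.2.2, outcomes | Only pregnancies arising while enrolled |
| Table 3, footnote n | Special Situations and serious events start at consent |
| Table 3 row label and 9.3.2.5 | Retrospective form, labelled for disease-related events |
| 11.2.1 | Retrospective adverse events collected back to first marketed dose |
| 11.2.2 with 11.1.3 and 11.1.3.1 | Retrospective serious events and Special Situations included, hence losses, terminations and exposure in pregnancy |

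Footnote n and section 11.2.2 cannot both hold for Special Situations before consent. The form's label also does not fit the content that section 11.2.2 gives it.

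**2. Three cases traced through the text**

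- *Loss or termination before consent.* It has a route as a serious event (11.1.3.1 with 11.2.1 and 11.2.2), against the form's label and footnote n. No section asks for conception date, last dose date or the pregnancy form.
- *Uncomplicated live birth completed before consent.* It is not on the list of serious outcomes. Only the Special Situation reading of 11.2.2 would bring it in, and no infant follow-up is stated. This is the weakest route.
- *Pregnancy ongoing at consent.* Exclusion criterion 2 in section 9.2.1.2 lets in participants who stopped palovarotene during the pregnancy, for safety follow-up.

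**3. Effect on incidence if pre-consent time is counted without its pregnancies**

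Assumptions, none from the documents: half the women are non-naïve, follow-up averages 4 years, the pregnancy rate is constant, and no pre-consent pregnancy is captured. With g years on drug before consent, the uncovered share of exposed time is 0.5g / (0.5g + 4).

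- g = 0.5: 0.25 / 4.25 = 5.9%
- g = 1.5: 0.75 / 4.75 = 15.8%
- g = 3: 1.5 / 5.5 = 27.3%

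Incidence is understated by that share. It is less if some pre-consent pregnancies arrive through 11.2.2, and nil if person-time starts at consent.

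**4. Which pregnancies would already have ended by consent**

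Assume conceptions spread evenly over T weeks from first marketed dose to consent, with each pregnancy lasting L weeks. The share ended by consent is max(0, (T − L)/T).

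| T (weeks) | L = 8 | L = 12 | L = 38 (term) |
|---|---|---|---|
| 26 | 69% | 54% | 0% |
| 52 | 85% | 77% | 27% |
| 104 | 92% | 88% | 63% |
| 156 | 95% | 92% | 76% |

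Early-ending pregnancies are always over-represented, but over long gaps most term pregnancies have ended too. For the mix, take T = 78 (1.5 years), early endings at 9 weeks and the rest at 39. The ended shares are 69/78 = 88% and 39/78 = 50%.

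- 30% early-ending: 0.3 × 0.885 = 0.265 against 0.7 × 0.5 = 0.350, so 0.265/0.615 = 43% of those ended are early.
- 50% early-ending: 0.442 against 0.250, so 0.442/0.692 = 64%.

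**5. Pregnancies still ongoing at consent**

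With the same durations these are length-biased. Early-ending ones make up 0.3 × 9 / (0.3 × 9 + 0.7 × 39) = 9.0% instead of 30%, or 0.5 × 9 / (0.5 × 9 + 0.5 × 39) = 18.8% instead of 50%. They should not be pooled with pregnancies observed from their start.

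**The case against.** The strongest answer is that the protocol does provide for these pregnancies. Losses and terminations are serious events, exposure in pregnancy is a Special Situation, and section 11.2.2 counts both among retrospective important medical events. That is correct. A reader might infer from section 11.1.3.1 alone that pregnancies ending before consent are simply missed, and that these are mainly early losses and terminations. The documents support neither inference. Losses have a clearer route than live births, and early endings are 43% or 64% of the ended pregnancies in step 4, depending on assumptions that the documents do not settle.

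The outcome objectives are also prospective by design. A pregnancy that begins after consent is seen from its start, so its outcome profile is not distorted by the gap. That stands too, and it rules out saying that the planned outcome summary as a whole looks better than it should.

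The blank retrospective cell in Table 3 is weak evidence taken alone, because the only pregnancy row there is for testing. The bias in incidence is conditional: section 9.7.3.4 states no person-time denominator, and the SAP, which is not shown, may fix one.

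The objection does not remove the conflict. Section 11.2.2 governs reporting to pharmacovigilance and exempts cases already reported spontaneously. It does not say that conception date, last dose or outcome enters the registry. Reaching capture means inferring across several sections, against the form's label and footnote n. An SAP cannot recover data that sites were not clearly asked to collect.

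**Conclusion.** The point holds as a conflict between sections with a gap in required detail. It does not hold as a finding that pre-consent pregnancies are excluded. Sections 11.1.3.1 and 9.3.2.5 and Table 3 with footnote n point towards no collection, or disease-related events only. Sections 11.2.1 and 11.2.2, read with 11.1.3 and the serious-outcome list in 11.1.3.1, point towards partial collection. No section clearly requires pregnancy details for the interval, and an uncomplicated live birth completed before consent is least protected.

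If pre-consent time on drug enters the incidence without its pregnancies, incidence is understated, by about 6% to 27% on the assumptions in step 3. Those percentages rest on assumed non-naïve share, gap and follow-up, and on no retrospective capture. Absolute numbers will be small. The change is still worth making, because the drug is teratogenic, exposed pregnancies will be few and the remedy is cheap.

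**What to change.** 1. Reconcile Table 3 (row label and footnote n), 9.3.2.5, 11.1.3.1, 11.2.1 and 11.2.2, so that they agree on what is collected between first marketed intake and consent.
2. In Table 3 and section 11.1.3.1, add a Baseline item for non-naïve participants recording every pregnancy since first marketed intake, with conception date, last dose date and outcome.
3. Report these pregnancies separately as retrospective, apart from those followed prospectively.
4. In section 9.7.3.4, start the person-time for pregnancy incidence where ascertainment starts.

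The cost is one eCRF item, one table row and wording changes. The downside is reliance on recall and records for a few past pregnancies, which separate reporting keeps visible.

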### Breastfeeding

Breastfeeding is contraindicated to palovarotene use. No data are available on the presence of palovarotene in human milk, or the effects of palovarotene on the breastfed child, or on milk production. Because of the potential for serious adverse reactions from palovarotene in a breastfed child, lactating women should not breastfeed during treatment with palovarotene.

Any use of an Ipsen product during lactation/ breastfeeding must be collected on the electronic data collection tool or the "Adverse Event and Other Safety Events Report Form for Company-Sponsored Non-Interventional Studies" (134232-FOR) if the electronic data collection tool is unavailable.

**PAGE 78 OF 287** 

11.1.3.2 Overdose, Off-label Use, Misuse, Abuse, Occupational Exposure, Medication Error, Lack of Effectiveness, and other Special Situations

#### Overdose

Any dose higher than the maximum recommended dose in local label/SmPC. For products which require gradual titration, any dose (initial or maintenance) which is higher than the recommended regime or labelling text will be assessed as 'overdose'. Overdose should be reported in the Special Situations eCRF page whether or not it was associated with an AE. If the Special Situation is associated with an AE, the AE should be reported in the AE eCRF page and AE number should be mentioned in the Special Situations eCRF page. All overdoses should be reported to Ipsen within 7 calendar days using the electronic data collection tool or the "Adverse Event and Other Safety Events Report Form for Company-Sponsored Non-Interventional Studies" (134232-FOR) if the electronic data collection tool is unavailable.

